### 3 Abbreviations and definitions of terms

BMI	Body Mass Index
Clinically relevant differences	Definitions of clinically relevant differences for all hypothesis-related outcomes will be reported in a statistical analyses plan (SAP). The SAP will be written and uploaded to clinicaltrials.gov before the statistical analyses will be conducted.
DDQOL	Diabetes Diet-related Quality of Life
DTSQ	Diabetes Treatment Satisfaction Questionnaire
EMR	Electronic Medical Record
GA	Gestational age
GDM	Gestational Diabetes Mellitus
HbA1c	Glycosylated haemoglobin A1c
HCCQ	Health Care Climate Questionnaire
Jaundice	Neonatal jaundice or neonatal hyperbilirubinemia is defined as elevated total serum bilirubin (TSB) (>68-137 $\mu\text{mol/l}$ ) and clinically manifests as yellowish discoloration of the skin, sclera, and mucous membrane.
LGA	Large for gestational age
Macrosomia	Macrosomia or foetal overgrowth is defined as birth weight >4,500 g
Neonatal hypoglycaemia	Neonatal hypoglycaemia is defined as plasma glucose level < 2.5 mmol/l after the first 2 postnatal hours.
NICU	Neonatal Intensive Care Unit
Non-white ethnic minority background	Non-white ethnic minority groups are defined as groups belonging to minority populations of non-European origin characterised by their non-white status. These include Asian (Indian, Pakistani, Bangladeshi, Chinese, any other Asian background), Caribbean, Black, African, Middle East, Hispanic/Latino, and any mixed or multiple ethnic background (1).
OGTT	Oral Glucose Tolerance Test.
PCDS	Perceived Competence in Diabetes Scale
PPAQ	Pregnancy Physical Activity Questionnaire
Preeclampsia	Preeclampsia is defined as new-onset gestational hypertension (with a blood pressure $\geq 140/90$ mmHg after 20 weeks of gestation in combination with proteinuria ( $\geq 0.3$ g protein in 24-hour urine specimen or $\geq 0.1$ g protein in a midstream urine spot), pulmonary oedema and/or specific symptoms of significant end-organ dysfunctions (e.g., headache, nausea, vomiting).
Preterm birth	Preterm birth is defined as GA less than 37 completed weeks
SD	Standard deviation
SGA	Small for gestational age
SOP	Standard operational procedure
Telemedicine	Telemedicine consultations are defined as tele- or video consultation
V	Visit
White ethnic background	White origin is defined as people with European ancestral origins who identify, or are identified, as white (also called European, or in terms of racial classifications, the group known as Caucasian). The term derives from the concept of race but is used as an indicator of ethnicity(1).
WHO-5	The WHO-Five Wellbeing Index (WHO-5) to assess wellbeing

## 4 Introduction

### 4.1 Background

#### 4.1.1 Prevalence and ethology

The prevalence of gestational diabetes (GDM) is increasing in parallel with the global epidemic of obesity, both worldwide and in Denmark. GDM now affects around 6% of all pregnancies in Denmark (2), and 14% of pregnancies worldwide (standardised estimation) ranging from 8% in North America and Europe, 10% in South and Central America, 14% in Africa, 21% in South-East Asia to 28% in Middle East and North Africa (3). Higher risks of GDM have been reported in immigrants from Non-Western countries living in Denmark, reflecting ethnic differences in the prevalence of GDM (4).

GDM is defined as glucose intolerance with onset or first recognition during pregnancy (5). The disease is characterized by hyperglycaemia and a marked insulin resistance secondary to placental hormonal release (6). Risk factors for developing GDM in pregnancy include obesity, excessive gestational weight gain, previous GDM, glucosuria, family history of diabetes, ethnicity, and hypertension (6). Hyperglycaemia is associated with serious short- and long-term complications for mother and child including delivering large-for-gestational-age (LGA) babies, macrosomia (birth weight >4,500 g), preterm birth, caesarean section, preeclampsia, birth injury (e.g., shoulder dystocia), respiratory distress syndrome, neonatal hypoglycaemia, jaundice, and increased admission to neonatal intensive care unit (NICU) (7). Finally, hyperglycaemia during pregnancy also increases the long-term risk of obesity, type 2-diabetes (T2D), and cardiovascular disease both in the mother and the offspring later in life (6).

#### 4.1.2 Dietary therapy

First-line treatment in GDM after diagnosis is dietary therapy including a systematic and detailed dietary assessment to identify relevant areas for adjusting the diet and overall lifestyle (e.g., increasing physical activity). The overall goals with dietary therapy are 1) To provide adequate calories and micro- and macronutrients to meet the needs of pregnancy consistent with maintaining normoglycaemia, 1) To improve glycaemic control; and 3) To secure appropriate gestational weight gain and avoid excessive weekly gestational weight gain (6, 8). In addition to dietary therapy, women are trained in self-monitoring blood glucose (SMBG) to assess if glycaemic targets are met. The American Diabetes Association (ADA) recommends continuous dietary adjustments based on the women's regularly measured blood glucose, appetite, weight-gain patterns, changes in dietary preferences, exercise patterns, and overall life situation (e.g., work and leisure time versus maternity leave changes affecting diet and physical activity) (6).

Most pregnant women are screened and diagnosed with GDM between 24-28 weeks of gestation. This leaves a very short window for dietary intervention to improve blood glucose control and limit body weight gain during pregnancy. Currently, no evidence exists for specific recommendations concerning the optimal frequency, intensity, or duration of visits with a dietitian for improving maternal, foetal, or neonatal outcomes (6, 9). National clinical guidelines for treatment of GDM recommends up to three visits with a dietitian depending on the time of diagnosis (10). However, in the latest national clinical guidelines under review this has been changed to only one visit (11). Real-world data show that women with GDM are only seen once by a dietitian during pregnancy at Danish hospitals (unpublished data).

In some international clinics, dietitians review women with GDM again prior to starting insulin (the second-line treatment in GDM) to see whether any dietary modifications can be made so that insulin therapy may be averted (12). ADA also recommends telehealth visits including feedback systems for women with GDM to improve outcome compared with standard in person care based on high evidence(6, 13).

Kurtzhals et al. found that women with GDM with a lower weekly gestational weight gain from time of diagnosis and throughout dietary therapy, reflecting higher dietary adherence, was associated with improved maternal and neonatal outcomes including lower late-pregnancy HbA1c and healthier foetal growth (14). Based on clinical experiences most women with GDM are highly motivated for behavioural changes to protect the health of their unborn child (14). But with only one visit with a dietitian after diagnosis, the women are left much on their own to assess when, where, and how to adjust their diet most appropriately to meet targets for glycaemic control and body weight management while securing sufficient intake of micro- and macronutrients. In semi-structured interviews with 20 women with GDM of different ethnicity conducted in the Department of Obstetrics, Herlev Hospital, Autumn 2022, most of the women experienced being left much on their own after diagnosis and missed having more intensive dietary support (unpublished data).

#### 4.1.3 Insulin therapy

In most cases dietary improvements are sufficient to achieve glycaemic goals but in some cases insulin therapy is needed (6, 10). The need for initiating insulin therapy is assessed by the obstetrician at regular visits based on the woman's pre- and postprandial blood glucose, and ultrasonographic evaluation of foetal growth/abdominal circumference (10). The exact proportion of women with GDM requiring insulin therapy is not well-described due to lack of valid register-based data (incorrect use of diagnosis codes, and supply of insulin directly from the hospitals). One Danish cohort study found that the proportion of women with GDM requiring insulin therapy to be 27% during the reported period 2004 – 2016 (15). Another Danish cohort study reported that 32% of women with GDM were treated with insulin during the reported period 2011 – 2017 (14). No changes in diagnostic criteria for GDM have been made in Denmark during the reported periods. Based on data from Herlev Hospital, we found that 30% of women with GDM had been treated with insulin in 2019 – 2022 (unpublished data).

Several studies have tried to identify patient characteristics and predict failure of dietary therapy and need for insulin therapy (12, 14, 16-18). Factors include higher pre-pregnancy body mass index (BMI); BMI at diagnosis; previous GDM; higher haemoglobin A1c (HbA1c) at diagnosis and in late pregnancy; higher 2-hour glucose level on an oral glucose tolerance test (OGTT); lower gestational age (GA) at diagnosis; and higher weekly weight gain during pregnancy. The percentages starting insulin therapy also vary significantly according to ethnicity as shown in a retrospective review of five ethnic groups (South-East Asian, South Asian, Middle Eastern, Anglo-European and Pacific Islander) (19).

Insulin therapy can improve glycaemic control and has been shown to be effective in reducing the rate of macrosomia in GDM (20). But use of insulin during pregnancy is also associated with several clinical implications (e.g., increased risk of maternal hypoglycaemia) (6, 14, 21), increased hospital costs (endocrinologist visits, extra visits to other health care professionals, additional ultrasonographic examinations depending on the time of insulin initiation), and medical costs (insulin) (22) as well as higher costs in relation to delivery (e.g., induction of labor, pre-term delivery) (14), and neonatal care (increased risk of neonatal hypoglycaemia) (23, 24). Finally, the personal burden associated with insulin

use (e.g., extra worries, additional SMBG measurements, and insulin injections every day) also affects women with GDM (25). Only one smaller case-control study has looked at quality of life (QoL) in GDM and found no differences between the diet-treated vs. insulin-treated group (26).

#### 4.1.4 Nutrition recommendations

There is no clear consensus on an ideal dietary composition in GDM. A Cochrane review from 2014 examined the evidence for different dietary approaches and ended up concluding that all the studies for comparisons of maternal and infant health outcomes were too small for reliable conclusions about which type of dietary recommendations are most suitable for women with GDM (27). In a systematic review and meta-analysis for maternal glucose control and neonatal outcomes in GDM, it was found that modified dietary interventions (including low glycaemic index diets; low- versus high-carbohydrate diets; fibre-enriched diet; Dietary Approaches to Stop Hypertension (DASH)-diet; moderate energy restriction diet; high monounsaturated/polyunsaturated fatty acids diets; soy protein diets; personalised diet; ethnic meal plan diet) were associated with lower infant birth weight and less macrosomia. These associations were found despite a high heterogeneity between studies indicating that several methods can be used, and that dietary education and support should be individualised (28).

Since carbohydrate is the main energy-contributing nutrient in our diet with the highest impact on postprandial blood glucose levels (and a significant impact on the total energy balance), awareness concerning the intake of carbohydrate-rich food sources constitutes an important aspect of dietary therapy in GDM. Carbohydrates make up approx. 45% of total daily energy intake (E%) in the traditional Danish diet (29) which is in the lower end of the range of recommended intake in GDM (46-60 E%) (8). Institute for Medicine (IOM) and ADA recommends a minimum of 175 g of carbohydrates daily ( $\approx 35\%$  of 8,400 kJ/2,000 kcal per day) for normal pregnant women and for women with GDM to ensure appropriate glucose for normal foetal growth and cerebral development and function (6). However, the amount, type and distribution of carbohydrate intake varies greatly between different ethnic and cultural groups with the highest carbohydrate intake ( $>60\%$  E%) in traditional South-Asian, East-Asian, and African diets (30).

The total amount of carbohydrates consumed in a meal is a major predictor of the postprandial glucose response. However, both the quantity and quality (i.e., intake of dietary fibre, added sugar and glycaemic index) of carbohydrates influence blood glucose levels (6, 8). Thus, monitoring the dietary intake of carbohydrates continuously is important to control postprandial glucose fluctuations. This may lead to clinical benefits such as a reduction in the need for insulin, limit gestational weight gain, and potentially reduce foetal overgrowth, neonatal hypoglycaemia, and admission to NICU.

Health literacy especially among women from non-White ethnic minority groups are highly variable, and this may have a significant impact on GDM management including adherence to dietary therapy (31). Furthermore, migrants in Western society may also face huge challenges in managing their GDM due to language barriers. For example, some studies have shown that women living in English-speaking countries predominantly speaking other languages than English, have lower rates of dietary understanding compared with their English-speaking counterparts. This may also affect dietary adherence (32). Thus dietary recommendations must be culturally sensitive (4) and not based on Western ideas of what ideal meals should include to support dietary adherence and glycaemic control.

In summary, the most optimal way to deliver dietary therapy to women with GDM is not known. The possibility that intensive dietary therapy may reduce the need for initiating insulin treatment without increasing hospital service costs for these women in comparison with women receiving standard dietary care needs to be explored.

## 4.2 Objective

The overall objective is to investigate the effectiveness and hospital service costs of implementing an intervention with intensive dietary counselling and support during pregnancy in women with GDM.

## 4.3 Specific objectives

The overall objective is to investigate differences in clinical, cost-related, and patient-reported outcomes between women with GDM randomised to either intensive dietary therapy or standard dietary care.

The specific objectives are:

1. To investigate the effect of intensive dietary therapy on the likelihood of remaining treated with diet only vs. needing insulin therapy based on a hypothesis hierarchy (main objective)
2. To investigate the effects on maternal outcomes: changes in gestational weight gain; glycaemic control (HbA1c); gestational age at insulin initiation and prescribed insulin dose
3. To investigate the effects on neonatal outcomes: changes in birth weight; birth weight standard deviation score; neonatal hypoglycaemia; and admission to NICU
4. To describe changes in other pregnancy outcomes: number of cases of preeclampsia; preterm birth; mode of birth (caesarean section); jaundice; and macrosomia
5. To describe changes in patient-reported outcomes: treatment satisfaction; well-being; diet-related quality of life; autonomy support; and health competencies
6. To describe changes in dietary intake and physical activity
7. To describe if the intervention was conducted as planned, including number and type of visits
8. To describe hospital service costs related to the intensive dietary intervention compared with standard care in a cost-analysis.

## 4.4 Hypotheses

1. Hypothesis hierarchy for the primary outcome (objective 1):  
The type I error will be controlled in the strong sense using the following hierarchical (fixed sequence A-C) testing procedure. This is based on priority ordering of the hypotheses and testing them in this order until an insignificant result appears:
  - A. We hypothesise that intensive dietary therapy is superior to standard dietary care (control group) in reducing the need for initiating insulin therapy in all women with GDM. Superiority will be claimed if the difference between the two groups is equal to, or surpass, the minimal important difference (defined as 50% reduction in need for initiating insulin therapy in the intervention group compared with the control group) in favour of the intensive treated group, and if the P-value is  $< 0.05$ .
  - B. We hypothesise that intensive dietary therapy is superior to standard dietary care (control group) in reducing the need for insulin therapy in women with a white ethnic background with GDM. Superiority will be claimed if the difference between the two groups is equal

- to, or surpass, the minimal important difference (defined as 50% reduction in need for initiating insulin therapy in the intervention group compared with the control group) in favour of the intensive treated group, and if the P-value is  $< 0.05$ .
- C. We hypothesise that intensive dietary therapy is superior to standard dietary care (control group) in reducing the need for initiating insulin therapy in women with GDM with a non-white ethnic minority background. Superiority will be claimed if the difference between the two groups is equal to, or surpass, the minimal important difference (defined as 50% reduction in need for insulin therapy in the intervention group compared with the control group) in favour of the intensive treated group, and if the P-value is  $< 0.05$ .
2. Hypotheses for secondary outcomes (objective 2 and 3):
- We hypothesise that an intensive dietary intervention in comparison with standard dietary care will induce:
    - a clinically relevant limitation in gestational weight gain
    - a clinically relevant improvement in HbA1c
    - a clinically relevant delay in insulin therapy initiation
    - a clinically relevant limited maximal insulin dose (units per kg body weight)
    - a clinically relevant reduction in birth weight at delivery at term
    - a clinically relevant reduction in birth weight SD at delivery
    - a clinically relevant reduction in neonatal hypoglycaemia
    - a clinically relevant reduction in new-borns admitted to NICU
3. Objectives 4-7 are regarded descriptive
4. Hypothesis for hospital care costs related to the intensive dietary intervention (objective 8):
- We hypothesise that an intensive dietary intervention in comparison with standard dietary care will have a positive effect on the net hospital costs, or at least be cost neutral (non-inferiority) if insulin therapy can be prevented for some of the women. The reason being that insulin therapy is associated with more cost intensive GDM treatment during pregnancy, higher expenses for inducement of labour, and higher cost of adverse events for mother and child as caesarean section and NICU stay, and length of hospital stay. The cost will be estimated from referral with GDM to discharge of mother and offspring.

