## 8 Sample size determination

A 50% difference in the incidence of insulin therapy between the two study groups during the study period was defined as the minimally important difference for the primary outcome. The sample size estimation was based on a logistic regression model (outcome = group) and the following assumptions: An allocation ratio of 1:1; alpha = 0.05; 0.8 power, an incidence of insulin therapy of 30% in the usual care group and 15% in the intervention group in need of insulin therapy. The expected incidence in the standard care group is based on register data from Herlev Hospital in the period 2019-2022 showing that approximately 30% of the women with GDM referred to the hospital had been prescribed insulin. Since we are only investigating women with GDM with an estimated risk of insulin therapy above 20% based on our inclusion criteria), our analysis shows that it will result in an incidence of 50%. Thus, we aim to include 214 women (see table 3 for sample size estimations), but if fewer women are included, we will only test the main hypothesis for all participants whereas subgroup-analysis testing based on ethnicity (white\_nonwhite) will be exploratory.

**Table 3:** Sample size estimations

N Total	Power All	Power Subgroups
107	0.80	0.51
150	0.92	0.65
175	0.95	0.72
200	0.97	0.78
214	0.98	0.80

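### The A-B-C fixed sequence is valid, but making the non-white hypothesis wait for the white one costs it power that strong error control does not require

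*Protocol*

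**What the plan says.** Section 4.4 sets three hypotheses on insulin initiation: A in all women, B in women of white background, C in women of non-white minority background. It says "The type I error will be controlled in the strong sense using the following hierarchical (fixed sequence A-C) testing procedure", and then "This is based on priority ordering of the hypotheses and testing them in this order until an insignificant result appears". For each hypothesis, superiority is claimed only if P < 0.05 and the observed reduction is at least 50%.

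Section 8 gives the planning inputs: "An allocation ratio of 1:1" and "alpha = 0.05; 0.8 power". A 50% difference "was defined as the minimally important difference for the primary outcome". Section 8 first quotes 30% versus 15%, then says of the population selected for a predicted risk of at least 20% that "our analysis shows that it will result in an incidence of 50" per cent. Table 3 gives power of 0.98 for all women and 0.80 for subgroups at N = 214. It gives no joint power for the sequence. The section also limits the subgroup tests: "if fewer women are included, we will only test the main hypothesis for all participants", and the ethnic subgroups are then exploratory.

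**The concern.** Under the stated order, a chance miss in white women closes the test in non-white women whatever their data show. That would be a fair price if the family-wise error rate depended on it, but it does not. By Table 3, 107 women already give 0.80 power for A, and the increase to 214 brings the subgroups to 0.80. The extra recruitment therefore serves mainly B and C, and the sequence gives part of that benefit away for C. Sections 4.1.3 and 4.1.4 stress ethnic differences in insulin use, diet and adherence, so a confirmatory result in non-white women is a real aim of the trial.

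**Working it through.** **Inputs.** Two-sided 0.05 (section 8 gives 0.05; sidedness is not stated and two-sided is assumed), 1:1 allocation, N = 214. The control rate is 50% (section 8). The intervention rate of 25% is derived from the 50% reduction. Equal subgroups of 107 are not stated but are implied by Table 3, where overall power at N = 107 equals subgroup power at N = 214 (both 0.80).

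**Reproducing Table 3.** Power = Φ(0.25 / √[(0.5·0.5 + 0.25·0.75)/n] − 1.96), with n per arm.
- All women, n = 107: 0.25/0.0639 = 3.91; 3.91 − 1.96 = 1.95; power 0.974 (table 0.98).
- Subgroup, n = 53.5: 0.25/0.0904 = 2.76; 2.76 − 1.96 = 0.80; power 0.789 (table 0.80).

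Every row of the table agrees within 2 points. Rates of 30% versus 15% give 0.75 and 0.46 and do not reproduce it.

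**Is the B-to-C step needed for strong control?** There are three cases when A alone opens B and C.
1. B and C are both true nulls. Under randomisation A is then also a true null, and any false claim must first reject A, which has probability at most 0.05.
2. A is a true null for another reason (opposite effects). Any false claim again requires rejecting A.
3. A is false. At most one of B and C is a true null, and it is tested at 0.05.

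Simulated error with A opening both, equal halves:
- Global null: A is rejected with probability 0.047.
- Only C null, B effective: 0.026.
- Only B null, very large effect in C: 0.040.

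One extreme setting (64 white women, very strong effect in C) gave 0.054, but under both procedures alike. It comes from the discreteness of the z-test, not from the gating.

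**Power for C at equal halves.** If B and C are both significant in the same direction, Z_A ≈ (Z_B + Z_C)/√2 is at least 3.92/1.414 = 2.77, so A is significant too. Hence P(A, B and C) ≈ P(B)·P(C).
- From the table's 0.80: in sequence 0.80 × 0.80 = 0.64; with A opening both, P(A and C) = 0.797. Loss about 16 points.
- From the pooled formula (0.769): in sequence 0.769² = 0.591; with A opening both, 0.765. Loss 17 points. Binomial simulation agrees (0.591 and 0.766).

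Power for A, and for B after A, is the same under both schemes.

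**Other ethnic splits**, same effect in both subgroups, N = 214:

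| White share | C, A opens B and C | C, A-B-C sequence | Loss, simulated (points) | Loss, scaled to Table 3's 0.80 |
|---|---|---|---|---|
| 30% | 0.89 | 0.49 | 40 | 38 |
| 40% | 0.84 | 0.57 | 27 | 25 |
| 50% | 0.77 | 0.59 | 17 | 16 |
| 60% | 0.67 | 0.57 | 10 | 9 |
| 70% | 0.55 | 0.49 | 5 to 6 | 5 |

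**With the 50% observed-reduction rule**, equal halves: if significance alone opens the next step, C falls from about 0.51 to 0.39. If the rule also applies at each earlier step, C falls from 0.39 to 0.26. The loss is 11 to 13 points.

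**Unequal effects**, equal halves, white women at 50% versus 25%: with non-white women at 50% versus 30%, 35% or 40%, the loss is 12.6, 7.7 or 3.9 points. Conversely, with no effect in white women and the planned effect in non-white women, C is reached and significant with probability 0.43 when A opens both and 0.02 in sequence.

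**The case against.** The strongest reply is that nothing in section 4.4 is false. A fixed sequence is a standard method, it was prespecified, and the order rests on a stated priority. A reader might infer from this point that the protocol's error control fails. It does not: the sequence controls the family-wise error as claimed. The priority argument, however, does not justify the gate, because B has the same alpha and the same power whether or not C waits for it.

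A reader might also take 17 points as a fixed loss. The documents do not support that. The figure needs equal subgroups and the planned effect in both. Section 4.1.4 itself names language barriers and variable health literacy that could weaken adherence, and so the effect, in non-white women, which would shrink the loss. The 30% white case departs from the split that Table 3 implies. The 50% rule limits C as well: even with the change, C reaches only about 0.4 to 0.5 when that rule is counted.

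Nor does the gate do literally nothing. With C null and B effective, it lowers the false-claim rate for C from 0.026 to 0.020. That is a real but small effect, and both figures are below 0.05.

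Finally, the gate has no effect if fewer than 214 women are included, and a blocked C loses only its confirmatory status. The estimate and interval for non-white women can still be reported.

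**Conclusion.** The sequence is valid but needlessly inefficient. Letting A alone open B and C keeps strong control at 0.05, leaves A and B as they are and is never less powerful for C. At equal halves and 50% versus 25% the gain for C is about 16 to 17 points (0.64 to 0.80 from Table 3, 0.59 to 0.77 by simulation). It ranges from about 5 points at 70% white to about 40 at 30% white, and is 11 to 13 points at equal halves under the protocol's own 50% rule. The argument assumes that every randomised woman is classed as either white or non-white. The gain counts only if 214 women are included. This is a worthwhile improvement in efficiency, not the correction of an invalid test.

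**What to change.** In section 4.4, replace the A-to-C sequence with:

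> *A is tested first at two-sided 0.05. If A is significant, B and C are each tested at two-sided 0.05, independently of each other. Strong control follows from closed testing, because no effect in both subgroups implies no effect in all women. The gate is significance of A; the 50% criterion for claiming superiority applies to each hypothesis as now.*

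Use the same wording in the SAP. Leave in place the section 8 rule that makes the subgroup tests exploratory below 214 women.

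The change needs no patients and no data. Its cost is procedural: the trial is open-label, with recruitment planned from October 2023, so loosening a prespecified hierarchy must be recorded as a dated amendment before any comparison of outcomes by group. If such a comparison has already been made, the stated sequence should stand.

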## 4.5 Study endpoints

### 4.5.1 Primary endpoint

The primary endpoint is the percentage of women with GDM treated with insulin therapy in the intervention group and the control group at delivery.

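### Section 4.4 requires an observed reduction of at least 50% as well as P<0.05, but Table 3 gives power for P<0.05 only: at the design effect the chance of claiming A is about 52%, not 98%

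*Protocol*

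**What the plan says.** Section 4.4 gives one claim rule for all women (A), women of white background (B) and women of non-white minority background (C): "Superiority will be claimed if the difference between the two groups is equal to, or surpass, the minimal important difference". The minimal important difference is "defined as 50% reduction in need for initiating insulin therapy in the intervention group compared with the control group", and the rule adds that P must be below 0.05. Both conditions apply to the observed result.

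The three hypotheses form a fixed sequence: "This is based on priority ordering of the hypotheses and testing them in this order until an insignificant result appears".

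Section 8 uses the same threshold as its planning effect: "A 50% difference in the incidence of insulin therapy between the two study groups during the study period was defined as the minimally important difference". Power comes from a logistic regression of outcome on group at alpha 0.05. The stated rates are "an incidence of insulin therapy of 30% in the usual care group and 15% in the intervention group in need of insulin therapy". For women selected at 20% or higher predicted risk, the text then says "our analysis shows that it will result in an incidence of 50" per cent. Table 3 prints, at N=214, power of 0.98 for all women and 0.80 for subgroups. No figure is given for the chance of meeting the two-part rule.

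**The concern.** The assumed effect lies exactly on the claim threshold. If the true reduction is 50%, the estimate falls on either side of 50% about equally often, and a larger trial only narrows its spread around that same point. A reader who takes Table 3 as the chance that a true 50% reduction leads to a superiority claim would be misled by some 45 percentage points. The 214 women correspond to the row where subgroup power reaches 0.80, so the chosen size rests on a probability that the claim rule does not deliver.

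A smaller question follows. A result with P<0.05 and a reduction below 50% is significant, yet A is not claimed. Section 4.4 does not say outright whether B is then tested, and this outcome would be common.

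**Working it through.** **Inputs.** Section 4.4: claim if the observed reduction is at least 50% and P<0.05. Section 8: 1:1 allocation, alpha 0.05, N=214 (107 per arm), control rate 30% or, after selection, 50%. Assumptions: two-sided test; 25% in the intervention arm for the 50% control rate (inferred from the 50% reduction); the reduction is relative, on incidence; the two ethnic subgroups are of equal size.

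**1. Reproduce Table 3.** Normal approximation: power = Φ(|p1−p2| / √[(p1(1−p1)+p2(1−p2))/n] − 1.96).

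- 50% v 25%, n=107: 0.25/√(0.4375/107) = 3.91; Φ(1.95) = 0.974 (printed 0.98).
- 50% v 25%, n=53.5 (subgroup): 0.25/√(0.4375/53.5) = 2.76; Φ(0.80) = 0.789 (printed 0.80).
- 30% v 15%, n=107: 0.15/√(0.3375/107) = 2.67; Φ(0.71) = 0.761, which does not match.

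At 50% v 25%, all ten entries are reproduced within 2 points. Table 3 is therefore the power of the significance test alone.

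**2. Probability of the full rule.** Let x and y be the numbers on insulin in the control and intervention arms, n per arm. The 50% condition is y ≤ x/2, that is x − 2y ≥ 0. When p2 = p1/2, the mean of x − 2y is n(p1 − 2p2) = 0 for every n, so the condition holds with probability close to one half. The P-value hardly matters: with 54 of 107 controls on insulin, 39 in the intervention arm (a 28% reduction) is already significant.

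Exact enumeration of two binomials, 107 per arm, pooled score test:

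| True rates | P<0.05 | Full rule | P<0.05 but reduction below 50% |
|---|---|---|---|
| 50% v 25% | 0.970 | 0.524 | 0.970 − 0.524 = 0.446 |
| 30% v 15% | 0.759 | 0.529 | 0.759 − 0.529 = 0.230 |

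**3. The all-women column of Table 3 restated (50% v 25%).**

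| N | Printed | P<0.05, exact | Full rule |
|---|---|---|---|
| 107 | 0.80 | 0.77 | 0.51 |
| 150 | 0.92 | 0.90 | 0.53 |
| 175 | 0.95 | 0.94 | 0.51 |
| 200 | 0.97 | 0.96 | 0.52 |
| 214 | 0.98 | 0.97 | 0.52 |

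At 500 per arm the full rule still gives 0.51.

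**4. Subgroups and sequence at N=214.** Each subgroup rule taken alone gives 0.51–0.53 at 50% v 25% and 0.44–0.46 at 30% v 15%, against 0.80 printed. Through the sequence at 50% v 25% (1,000,000 simulated trials per setting):

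| Gate | B claimed | C claimed |
|---|---|---|
| P<0.05 | 0.51–0.53 | 0.39–0.42 |
| Full rule | 0.39–0.41 | 0.26–0.29 |

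**5. Other true effects, 107 per arm.** With a true reduction of 40%, P<0.05 has probability 0.85 and a claim 0.17 (control 50%), or 0.54 and 0.26 (control 30%). An 80% chance of claiming A needs a true reduction of about 57% (control 50%) to 60% (control 30%).

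**The case against.** **A demanding success criterion is the sponsor's right.** This stands. The rule is prespecified and conservative and does not inflate type I error, and the estimate and P-value can be reported whatever the claim. The fault is the mismatch with the stated power.

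**Table 3 is labelled power and is about right for the test it describes.** Also true. But it is the only support given for the sample size, and the same protocol fixes a different rule for claiming success.

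**The scale of the reduction is not named, and the planning model is logistic.** If the threshold were an observed odds ratio of 0.5, the joint probability would be 0.92 (50% v 25%) or 0.72 (30% v 15%). The text points the other way: section 8 speaks of a difference in incidence and illustrates it as 30% to 15%. That is a risk ratio of 0.5, whereas the odds ratio is (0.15/0.85)/(0.30/0.70) = 0.41.

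**More women would help.** Only if the true reduction exceeds 50%. At the planning effect they do not.

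**A SAP is promised.** Section 3 of the protocol leaves definitions of clinically relevant differences to a SAP posted before analysis, and that document may also settle how the gate works. Insignificant most naturally means P≥0.05, so the gate wording is a lesser point. The claim rule and Table 3, however, are both already fixed in the protocol and do not agree.

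**Conclusion.** The concern holds. Under the rule in section 4.4, a true 50% reduction leads to a claim of A with probability about 0.52, not 0.98. The result is nearly the same for either pair of rates in section 8 (0.524 or 0.529), so it does not depend on the inferred 25%. It does rest on reading the reduction as relative, on incidence, and on counting exact ties at 50% as success, as the rule does; without ties it is 0.486 at 50% v 25%. The subgroup and sequence figures further assume an equal ethnic split. The ambiguity about the gate is secondary, but at the design effect it concerns 23% to 45% of trials and should be closed.

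**What to change.** Choose one of two courses.

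- **Keep the two-part rule.** Restate Table 3 for it: about 0.52 for A at N=214, and 0.51–0.53 for each subgroup alone at 50% v 25% with an equal split, with the lower values through the sequence. State the rates used, including the intervention rate, and that the 50% is a relative reduction in incidence. Add one sentence to section 4.4 saying whether the gate is P<0.05 or the full rule. The cost is text only, plus a much less favourable table.
- **Change the rule.** Claim superiority, and pass the gate, on P<0.05 in favour of the intervention. Report the relative risk with its 95% confidence interval against the 50% benchmark as a judgement of clinical relevance. This relaxes the success criterion of an open-label trial, so it is acceptable only as a dated amendment made before anyone knows outcomes by group. If that can no longer be assured, take the first course.

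Neither course needs extra women or data.
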